### 11.3.2. Expedited Reporting Guidelines

Use the study protocol number and the protocol-specific subject ID assigned during study registration on all reports. Progression of the cancer under study is not considered an adverse event unless it results in hospitalization or death.

**Note: A death occurring within 90 days of the last administration of study agent requires both routine and expedited reporting, regardless of causality. Attribution to treatment or other cause must be provided.**

Death due to PD should be reported as **Grade 5 “Malignant neoplasm progression”** to be coded under the system organ class (SOC) “Neoplasms benign, malignant and unspecified (incl cysts and polyps)”. Evidence that the death was a manifestation of underlying disease (e.g., radiological changes suggesting tumor growth or progression; clinical deterioration associated with a disease process) should be submitted.

### Expedited Reporting Requirements for Adverse Events that Occur on Studies under an IND/IDE within 30 Days of the Last Administration of the Investigational Agent/ Intervention

#### FDA REPORTING REQUIREMENTS FOR SERIOUS ADVERSE EVENTS (21 CFR Part 312)

**NOTE:** Investigators **MUST** immediately (within 24 hours) report ANY Serious Adverse Events, whether or not they are considered related to the investigational agent(s)/intervention (21 Code of Federal Regulations [CFR] 312.64)

An AE is considered serious if it results in **ANY** of the following outcomes:

- 1) Death
- 2) A life-threatening AE
- 3) An AE that results in inpatient hospitalization or prolongation of existing hospitalization for  $\geq 24$  hours
- 4) A persistent or significant incapacity or substantial disruption of the ability to conduct normal life functions
- 5) A congenital anomaly/birth defect.
- 6) Important Medical Events (IME) that may not result in death, be life threatening, or require hospitalization may be considered serious when, based upon medical judgment, they may jeopardize the subject and may require medical or surgical intervention to prevent one of the outcomes listed in this definition. (FDA, 21 CFR 312.32; ICH E2A and ICH E6).

### 11.3.3. Routine Adverse Event Reporting

All AEs **must** be reported in routine study data submissions. **AEs reported expeditiously to the Sponsor and/or Sponsor's safety designee must also be reported in routine study data submissions.**

AE data collection and reporting, which are required as part of every clinical study, are done to ensure the safety of subjects enrolled in the studies as well as those who will enroll in future studies using similar agents. For this study the Adverse Event CRF is used for routine AE reporting.

### 11.4. Adverse Events of Special Interest in NT-I7

The following AEs are of special interest in subjects receiving NT-I7, as defined below and must be reported by the investigator expeditiously to the Sponsor and/or Sponsor's Safety designee irrespective of regulatory seriousness criteria and the relatedness to NT-I7.

Immune-related adverse event (irAE) is defined as an AE associated with drug exposure that is consistent with an immune-mediated mechanism of action when there is no clear alternate etiology. For events which are potentially immune-related, additional information such as serologic, immunologic, and histologic (biopsy) data and use of steroids or immunosuppressants will be used to support an irAE diagnosis.

- Potential drug-induced liver injury that includes an elevated ALT or AST  $\geq 3 \times$  ULN in combination with an elevated bilirubin  $\geq 2 \times$  ULN and, at the same time, an alkaline phosphatase (ALP)  $< 2 \times$  ULN; no other reason can be found to explain the combination of increased AST or ALT, and TBL, such as viral hepatitis A, B, or C; preexisting or acute liver disease; or another drug capable of causing the observed injury. (86)
- Conditions (regardless of grade) suggestive of an autoimmune disorder or immune-related adverse events (irAEs), including but not limited to hepatitis, pneumonitis, colitis, pancreatitis, endocrinopathies (including but not limited to thyroiditis, Type 1 diabetes mellitus, adrenal insufficiency), myocarditis, myositis/polymyositis, rheumatoid arthritis, vasculitis, neuritis, systemic lupus erythematosus, Sjogren's syndrome, multiple sclerosis, Guillain-Barre syndrome and myasthenia gravis
- Symptoms and signs suggestive of hypersensitivity, cytokine release, or infusion reaction syndromes with a different underlying pharmacological etiology
- Grade  $\geq 2$  diarrhea
- Grade  $\geq 2$  AST/ALT and Grade  $\geq 2$  total bilirubin elevation with constitutional symptoms
- Grade  $\geq 3$  hypoxia or dyspnea
- Grade  $\geq 2$  pleural effusion that is not due to the underlying disease (e.g., non-malignant pleural effusion)

### 11.5. Treatment of Overdose for NT-I7

For this study, an overdose of NT-I7 will be defined as any dose  $> 1440 \mu\text{g/kg}$ .

No specific information is available on the treatment of overdose of NT-I7. In the event of overdose, the subject should be observed closely for signs of toxicity. Appropriate supportive treatment should be provided if clinically indicated.

### 11.6. Events of Clinical Interest (ECI) in Pembrolizumab

Selected adverse events are also known as Events of Clinical Interest (ECI) and must be reported to the Sponsor within 24 hours.

Events of clinical interest in pembrolizumab studies include:

1. An overdose of pembrolizumab, as defined in Section 11.7—Treatment of Overdose, that is not associated with clinical symptoms or abnormal laboratory results.

2. An elevated AST or ALT lab value that is greater than or equal to 3X the upper limit of normal and an elevated total bilirubin lab value that is greater than or equal to 2X the upper limit of normal and, at the same time, an alkaline phosphatase lab value that is less than 2X the upper limit of normal, as determined by way of protocol-specified laboratory testing or unscheduled laboratory testing.\*

*\*Note: These criteria are based upon available regulatory guidance documents. The purpose of the criteria is to specify a threshold of abnormal hepatic tests that may require an additional evaluation for an underlying etiology. The study site guidance for assessment and follow up of these criteria can be made available. It may also be appropriate to conduct additional evaluation for an underlying etiology in the setting of abnormalities of liver blood tests including AST, ALT, bilirubin, and alkaline phosphatase that do not meet the criteria noted above. In these cases, the decision to proceed with additional evaluation will be made through consultation between the study investigators and the Sponsor. However, abnormalities of liver blood tests that do not meet the criteria noted above are not ECIs for this study.*

### 11.7. Treatment of Overdose for Pembrolizumab

For this study, an overdose of pembrolizumab will be defined as any dose of 1000 mg or  $\geq 5$  times the indicated dose.

No specific information is available on the treatment of overdose of pembrolizumab. In the event of overdose, the subject should be observed closely for signs of toxicity. Appropriate supportive treatment should be provided if clinically indicated.

### 11.8. Pregnancy

Although not an AE in and of itself, pregnancy as well as its outcome must be documented via the EDC system. Any pregnancy occurring in a subject or subject's partner from the time of consent to 90 days after the last dose of study treatment must be reported and then followed for outcome. If a subject inadvertently becomes pregnant while on study drug treatment, the subject will be immediately discontinued from study treatment. The site will contact the subject at least monthly and document the subject's status until the pregnancy has been completed or terminated.

The outcome of the pregnancy will be reported to the Sponsor without delay and within 24 hours if the outcome is a serious adverse experience/important medical event (e.g., death, abortion, congenital anomaly, spontaneous abortion, missed abortion, benign hydatidiform mole, blighted ovum, fetal death, intrauterine death, miscarriage, stillbirth or other disabling or life-threatening complication to the mother or newborn). Newborn infants should be followed until 30 days old.

The study investigator will make every effort to obtain permission to follow the outcome of the pregnancy and report the condition of the fetus or newborn to the Sponsor and/or Sponsor's safety designee **within 24 hours** of the investigator's knowledge of the event via the study EDC system.

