  - g. Creatinine  $\leq 1.5 \times \text{ULN}$  or Creatinine clearance (CrCl)  $\geq 30 \text{ mL/min}$  for subjects with creatinine levels  $>1.5 \times \text{ULN}$ . CrCl should be calculated per institutional standard.
  - h. INR and aPTT  $\leq 1.5 \times \text{ULN}$  unless subject is receiving anticoagulant therapy as long as PT or aPTT is within therapeutic range of intended use of anticoagulants
9. ECG demonstrating Fridericia's corrected QT interval (QTcF)  $< 470 \text{ ms}$ . Patients with QTcF  $\geq 470 \text{ ms}$  will require clearance by a local cardiologist.

10. Female subjects who are either postmenopausal for at least 1 year, are surgically sterile for at least 6 weeks; female subjects of childbearing potential must agree to remain abstinent (refrain from heterosexual intercourse) or to use dual methods of contraception for the duration of study treatment and for 120 days after the last dose of study treatment (pembrolizumab and/or NT-I7). Female subjects of childbearing potential (including women who have had a tubal ligation) must have a negative serum or urine pregnancy test within 72 hours prior to Cycle 1, Day 1. If the urine test is positive, or cannot be confirmed as negative, a serum pregnancy test will be required.
11. Non-sterile male subjects who are sexually active with female partners of childbearing potential must agree to remain abstinent (refrain from heterosexual intercourse) or to use highly effective method(s) of contraception for the duration of study treatment and for 120 days after the last dose of study treatment (pembrolizumab and/or NT-I7).
12. Meet the requirements for the intended stages and arms (disease specific inclusion criteria), as follows:

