## V7.0 incorporating Amendment 6, 26Oct2023

1. Pregnant, lactating or breastfeeding or expecting to conceive or father children within the study duration from screening through 120 days after the last dose of study treatment.
2. Receiving chemotherapy or any anti-cancer therapy with half-life <1 week within 30 days or 5 half-lives, whichever is shorter, prior to first dose of study treatment. Receiving treatment with immune CPIs, immunomodulatory monoclonal antibodies (mAbs), and/or mAb-derived therapies within 4 weeks prior to first dose of study treatment. **Note:** All AEs related to previous therapies, except alopecia, must be resolved to  $\leq$ Grade 1 or baseline. Subjects with  $\leq$ Grade 2 neuropathy may be eligible. Subjects with endocrine-related AEs Grade  $\leq$ 2 requiring treatment or hormone replacement may be eligible.
3. Has received prior radiotherapy within 2 weeks of start of study treatment. Subjects must have recovered from all radiation-related toxicities, not require corticosteroids, and not have had radiation pneumonitis. A 1-week washout is permitted for palliative radiation ( $\leq$ 2 weeks of radiotherapy) to non-CNS disease.
4. Has known active central nervous system (CNS) metastases and/or carcinomatous meningitis. Subjects with previously treated brain metastases may participate provided they are radiologically stable (without evidence of progression by repeat imaging (during screening) for at least 4 weeks prior to the first dose of study treatment and any neurologic symptoms have returned to baseline), have no evidence of new or enlarging brain metastases, and are not using systemic steroids for CNS symptom management for at least 14 days prior to first dose of study treatment.
5. Subjects who have not recovered from AEs (other than alopecia, vitiligo, neuropathy or endocrinopathy managed with replacement therapy) due to agents administered more than 4 weeks earlier (i.e., have residual toxicities  $>$ Grade 1).
6. Concurrent or previous other malignancy within 3 years of study entry, except cured basal or squamous cell skin cancer, transitional cell carcinoma of urothelial cancer, carcinoma in-situ of the breast or cervix.

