#### 4.5. Contraception

NT-I7 and pembrolizumab may have adverse effects on a fetus in utero. Furthermore, it is not known if NT-I7 or pembrolizumab has transient adverse effects on the composition of sperm.

Subjects should be informed that taking the study medication may involve unknown risks to the fetus (unborn baby) if pregnancy were to occur during the study. In order to participate in the study, subjects of childbearing potential must adhere to the contraception requirement from time of consent (or 14 days prior to the initiation of study medication for oral contraception) throughout the study period up to 120 days after the last dose of study treatment.

If there is any question that a subject of childbearing potential will not reliably comply with the requirements for contraception, that subject should not be entered into the study.

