#### 11.3.1. Time Period and Frequency for Collecting AE, SAE and Other Reportable Safety Event Information

- All AEs, SAEs and other reportable safety events that occur after the consent form is signed but before treatment /allocation must be reported by the investigator, if the event causes the subject to be excluded from the study or is the result of a protocol-specified intervention, including but not limited to washout or discontinuation of usual therapy, diet, or a procedure.
- All AEs from the time of treatment/allocation through 30 days following cessation of study treatment or starting of new anticancer therapy, whichever is earlier, must be reported by the investigator.
- All AEs meeting serious criteria, from the time of treatment/ allocation through 90 days following cessation of study treatment or initiation of new anticancer therapy, whichever is earlier, must be reported by the investigator.
- All pregnancies and exposure during breastfeeding, from the time of treatment/ allocation through 90 days following cessation of study treatment or initiation of new anticancer therapy, whichever is earlier, must be reported by the investigator.
- Additionally, any SAE brought to the attention of an investigator at any time outside of the time period specified above must be reported immediately to the Sponsor if the event is considered to be drug-related.

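### Pregnancy reporting stops at day 90 after the last dose, but the contraception window runs to day 120, so pregnancies on days 91–120 need not be reported or followed

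*Protocol*

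**What the plan says.** Two sections of the protocol govern pregnancy reporting. Section 11.8 says that a pregnancy in a subject or a subject's partner "from the time of consent to 90 days after the last dose of study treatment must be reported", and that its outcome must be followed. It then asks for at least monthly contact until the pregnancy ends and for newborns to be followed to 30 days of age. Section 11.3.1 sets the reporting periods for all safety events and covers "All pregnancies and exposure during breastfeeding, from the time of treatment/ allocation through 90 days following cessation of study treatment". Its end point has a second limb that 11.8 lacks: reporting runs "through 90 days following cessation of study treatment or initiation of new anticancer therapy, whichever is earlier, must be reported by the investigator".

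Four other places deal with avoiding pregnancy, and all use 120 days. Inclusion criteria 10 (female subjects) and 11 (male subjects with partners of childbearing potential) require abstinence or contraception "for the duration of study treatment and for 120 days after the last dose of study treatment". Exclusion criterion 1 in Section 4.2 bars subjects who expect to conceive or father children "within the study duration from screening through 120 days after the last dose of study treatment". Section 4.5 applies the contraception requirement "throughout the study period up to 120 days after the last dose of study treatment". It gives as reasons that both drugs may harm a fetus and that their effect on sperm is unknown. The synopsis repeats the inclusion and exclusion wording.

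**The concern.** The protocol's prevention period outlasts its collection period. A pregnancy that begins between day 91 and day 120 is one the protocol asks subjects to avoid because of possible drug effects. If it happens anyway, no section requires the site to report it, make the monthly contacts or follow the newborn.

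What is at stake is safety information. The protocol says the effects on a fetus and on sperm are uncertain, and any exposed pregnancy in this trial would be rare human evidence on that question. A site also has two mandatory reporting rules that do not match each other, so different sites may apply different windows.

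**Working it through.** No sample size, power or error rate is involved. The check sets the windows side by side and subtracts.

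| Place in protocol | Governs | Starts | Ends (days after last dose) |
|---|---|---|---|
| Inclusion 10 and 11 | Contraception | Study treatment | 120 |
| Exclusion 1 | No planned conception | Screening | 120 |
| Section 4.5 | Contraception | Consent | 120 |
| Section 11.8 | Pregnancy reporting and follow-up | Consent | 90 |
| Section 11.3.1 | Pregnancy reporting | Treatment/allocation | 90, or start of new anticancer therapy if earlier |

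**Step 1: the gap under 11.8.** Contraception end minus reporting end = 120 − 90 = 30 days (days 91 to 120). As a share of the post-dose window, 30/120 = 25%.

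**Step 2: 11.3.1 read alone.** If new therapy starts on day t, with t below 90, reporting under 11.3.1 ends on day t and the uncovered period is 120 − t. With t = 30, an assumed value for illustration, that is 120 − 30 = 90 days, or 90/120 = 75%.

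**Step 3: the two rules together.** Both are mandatory, so a pregnancy must be reported if either rule captures it. The joint end point is the later of day 90 (from 11.8) and the earlier of day 90 and day t (from 11.3.1). That is day 90 for every t, so the joint gap stays at 120 − 90 = 30 days. For example, a pregnancy on day 60 after new therapy on day 30 is outside 11.3.1 but inside 11.8. The start points work the same way: 11.8 begins at consent, so the later start in 11.3.1 leaves nothing uncovered.

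**Step 4: does anything else cover days 91–120?**
- The last item of Section 11.3.1 requires late reporting of serious adverse events, but only those that come to the investigator's attention and are considered drug-related. Section 11.8 says that a pregnancy is not in itself an adverse event. An uncomplicated pregnancy, or a serious outcome judged unrelated, is not caught.
- The survival calls in footnote 28 of the Schedule of Assessments ask about survival, new treatment and ongoing adverse events. Pregnancy is not among the items. The calls start 90 days after the day-90 safety visit, at about 90 + 90 = 180 days after the last dose.
- Section 6.6 ends the active study when the last subject completes the 90-day safety visit, so some subjects may have no later contact at all.

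**The case against.** The strongest defence is that the 90-day end point is deliberate. The version 7.0 entry in the Protocol Revisions table records that the 11.8 window was shortened from 120 to 90 days to agree with 11.3.1. Ninety days also matches the serious adverse event window and the last safety visit. Preventing pregnancy and collecting data serve different purposes, and a cautious contraception margin need not set the reporting period. Section 2.4.1.2.1 gives an NT-I7 half-life of 48 to 112 hours after single low doses in healthy volunteers. Ninety days is 90 × 24 = 2,160 hours, or at least 2,160/112 ≈ 19 half-lives.

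Part of this stands. The change was intended, and the documents do not show that exposure matters on days 91–120. They give no pembrolizumab half-life, so they cannot settle the question either way. It is also right that 120 days is a precautionary contraception window and not a demonstrated period of fetal risk.

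It does not remove the mismatch. The only reason recorded for the cut is agreement with 11.3.1, and the current texts still differ from each other on start and stop. The contraception criteria were left at 120 days, with possible fetal harm as their stated basis.

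Two stronger readings are tempting, and the documents support neither. A reader might infer from 11.3.1 that early new therapy leaves up to 75% or more of the window unreported. Section 11.8 has no such stop and applies independently, so this does not follow. A reader might also infer that pregnancies after day 90 can never be captured. The late serious-event rule would catch some serious outcomes, though only those known to the investigator and judged drug-related.

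**Conclusion.** The point holds as a 30-day mismatch. For days 91–120 after the last dose, 25% of the post-dose contraception window, pregnancies in subjects or partners are not required to be reported or followed, apart from drug-related serious events that reach the investigator. The differences between 11.8 and 11.3.1 on start point and new therapy are a conflict between two mandatory rules and add nothing to that gap.

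This rests on two readings: that both reporting sections bind, and that a pregnancy is placed in the window by when it begins. It takes no position on whether 90 or 120 days is the right length for contraception; the passages must be reconciled.

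The practical effect is small in number. Few pregnancies are expected and the documents give no rate. No efficacy endpoint, sample size or planned efficacy analysis is touched. The correction is still worth making, because the information lost concerns fetal safety and is cheap to collect.

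**What to change.** Use one pregnancy-reporting window in Sections 11.8 and 11.3.1: from consent to the end of the protocol's own contraception window (currently 120 days after the last dose), with no stop at new anticancer therapy. Tying the end to the contraception window keeps the sections aligned if the sponsor later changes that window.

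To make it work after the last scheduled safety visit, tell subjects at the 90-day visit to report any pregnancy, their own or a partner's, up to the end of the window. Then ask about it at the next planned contact, whether a survival call or follow-up imaging, where one occurs. The survival call alone is not enough: it falls at about day 180, Section 6.6 places it after progression or new therapy, and the last subjects may have no later contact.

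The cost is a change of wording in two sections, one instruction at an existing visit and one question at an existing contact. The downside is that, rarely, there will be an extra pregnancy to follow.

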### 11.9. Use in Nursing Women

It is unknown whether NT-I7 and/or pembrolizumab is excreted in human milk. Since many drugs are excreted in human milk, and because of the potential for serious adverse reactions in the nursing infant, subjects who are breastfeeding are not eligible for enrollment.

### 11.10. Secondary Malignancy

A *secondary malignancy* is a cancer caused by treatment for a previous malignancy (e.g., treatment with investigational agent/intervention, radiation or chemotherapy). A secondary malignancy is not considered a metastasis of the initial neoplasm.

All secondary malignancies that occur after treatment with the study agents must be reported to the Sponsor and/or Sponsor's safety designee within **24 hours** of the investigator's knowledge of the event via the study EDC system. Three options are available to describe the event:

- Leukemia secondary to oncology chemotherapy (e.g., acute myelocytic leukemia [AML])
- Myelodysplastic syndrome (MDS)
- Treatment-related secondary malignancy

Any malignancy possibly related to cancer treatment (including AML/MDS) should also be reported via the routine reporting mechanisms outlined in each protocol.

